5.3 Procedures

For clarity, the following section only describes activities planned for the first recruitment round. If a second round is necessary (see above), all activities will be held the following year in the NHs participating in this second round.

Randomisation:

Some responsible physicians work in multiple NHs; this could lead to contamination of the control group. Moreover, some NHs have multiple responsible physicians; these two factors lead to the apparition of clusters of physicians working in the same NHs and which could amplify contamination of the control group. To account for this factor, after inclusion and before randomisation, NHs will be clustered by physicians: all NHs sharing at least one physician will be placed in the same cluster. NHs sharing no physician with another will be placed in clusters of size one.

A random list of A (intervention) and B (control) will be used to allocate NHs clusters to groups. The list will be constructed by generating a random list of numbers comprised between 0 and 1, with uniform distribution; numbers below 0.5 will be assigned the letter A, the others the letter B. The list will be of the same length as the list of included NHs clusters, and will be generated using Stata version 14.1.

Given the variable size of the clusters, this may lead to the constitution of two groups of unequal size. However, given the relatively small size of expected clusters (the largest possible cluster we are aware of regroups eight NH; most clusters will only include two NHs), this should not lead to a dramatic unbalance between the two groups.

Intervention:

Pharmacists of the NHs assigned to the intervention group will take part in a course where the material for the quality circle module (slides, relevant scientific literature and guidelines) will be made available to them. The content of the course was developed at the CPC. It comprises an overview of the problems posed to older people by polypharmacy and the use of PIMs, an in-depth description of the process of deprescribing and of the challenges to enacting it, a selection of useful clinical tools, and a selection of guidelines to deprescribe specific therapeutic classes (for example, proton-pump inhibitors or cholesterol-lowering drugs).

In the two months following course completion, every NH in the intervention group will hold a QC session prepared by the pharmacist based on the course. This session will address both generalities about polypharmacy, PIMs and deprescribing, and an in-depth discussion of the guidelines for deprescribing therapeutic classes selected by the pharmacist on the basis of their use in the NH. It is to be noted that the data necessary to select the specific therapeutic classes discussed during the session are both routinely collected and analysed by the NHs' pharmacists, due to their participation in their respective cantonal pharmaceutical assistance programme.

At the end of the session, participants will be required to build a consensus for deprescribing specific therapeutic classes in the NHs. This consensus will then be enacted by the care team, according to their best clinical knowledge. In addition, the participants will be encouraged to think about the strategies to implement each deprescribing measures chosen for the consensus. Physicians will retain complete control over therapeutic choices for individual residents, including the choice to enact the consensus or not.

In addition, the pharmacist will be required to send the consensus with strategies to the other participants two weeks after the session, to include a specific chapter about deprescribing in their PAP annual report for 2017 and to discuss the implementation of the consensus during the presentation of this report to the NH team.

All consensus and implementation strategies chosen by the participating NHs will be collected by the investigators, compiled and, after anonymization, communicated to the participants during the first trimester of 2018.

Data collection:

Assessment of this project's outcomes will be made using anonymised data, provided by the CPC monitoring team. These data will comprise, for every NH and every year:

- Mission of the NH (geriatric, psycho-geriatric, or mixed);
- Number of beds in the NH;
- Mean age of NH residents;
- Gender repartition of the residents;
- Total number of days spent at the NH;

- Total number of days sent in the hospital;
- Total number of deaths in the NH;
- Designation, pharmacode, number of boxes and total cost of every drug used in the NH during the year.

Some data will be collected directly in the NHs; these data will be aggregated at the NH level:

- Total number of falls in the NH;
- Total number of residents having fallen, if available;
- Total number of falls having resulted in a hospital stay, if available:
- Total number of falls having resulted in supplementary care, if available;
- Total number of hospital stays, if available;
- Total number of residents having had an hospital stay, if available;
- Total number of hospital stays resulting from a demand of the GP, on-call GP or the resident's family, if available:
- Total number of restraint measures enacted during the year, if available.

All data will be collected on a yearly basis. Data collected directly at the NH will be collected by nurses, using a CRF hosted on the REDCap instance maintained by the École de Pharmacie Genève-Lausanne (University of Geneva). Its access will be restricted to the investigators.

Implementation evaluation:

To evaluate the implementation of the intervention, participants in the intervention group will be asked to fill a specific questionnaire at the end of the QC session (baseline) and after 12 months. The questionnaires at baseline are available in annexes 3 to 6. The questionnaires at 12 months will include an evaluation of the implementation strategies related to the local deprescribing consensus; as such, they are not elaborated to date, as those strategies will be elaborated by the participants during the QC session.

A supplementary questionnaire will be sent to the pharmacists to monitor the implementation process after the QC session within the first trimester of 2018 (see Annex 6).

A copy of each presentation support prepared by the pharmacists to lead the discussion within the QC session and the final version of each consensus with implementation strategies will have to be sent to the investigators. The presence of the specific chapter in the PAP annual report will also be checked.

Between 4 and 6 months after the QC session, the head nurse or his surrogate will be reach to evaluate the efficacy of each implementation strategies. A global feedback will be sent to each participants. After 12 months, the effectiveness of each consensus and implementation strategies defined during the QC session will be systematically asked.

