5.2 Recruitment and Screening

Participants will be recruited among the NHs currently taking part in their respective cantonal pharmaceutical assistance programmes. The investigators have direct access to these NHs and their respective pharmacists through their mandate for the monitoring of these two programmes.

All NHs of Vaud and Fribourg with a mainly geriatric mission and that have been part of the programmes for more than a year will be offered the possibility to participate in this study by direct mailing from the investigators. Pharmacists providing the pharmaceutical assistance for these NHs will also be directly informed, and nurses and physicians will be contacted through their respective professional societies. The approval of all partners (NH direction, head nurse, responsible physician and pharmacist) will be required for enrolment (see Annex 2 for agreement to participate).

In case of insufficient recruitment, a second recruitment round will take place in 2018. The NHs agreeing to take part in this second round will be randomised as described in section 5.3, page 13; those allocated to the intervention group will then hold a QC session between December 2018 and January 2019. Data of the two recruitment rounds will be pooled for analysis (see section 8.2, page 18).

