5.4 Methods of minimising bias

To account for the other influences on the prescribing practices of physicians, a controlled design has been chosen. Thus, external influence from medical literature, expert opinions, treatment guidelines or other sources should equally impact NHs in the intervention and control groups.

Randomisation will increase the likelihood that the characteristics of participating NHs are similar between the two groups. To account for the fact that some physicians are responsible for more than one NH, thus allowing for "bleeding" of the intervention between the two groups, randomisation will be clustered at the physician level (see section 5.3, page 13 for details).

Previous discussions with the prospective participants and their professional associations show that there is a great interest for deprescribing among partners. We fear that a purely controlled design will prevent the participation of some of the most interested NHs, thus minimising the effect of the intervention. To reduce this risk, we will offer the possibility to participants randomized to the control group to enact the intervention one year after the start of the study. At this point, all NH in the intervention group will have submitted to the intervention and its effects will have full deployed.

Finally, assessments of the study outcomes will be conducted while maintaining allocation blinding, ensuring that no analysis bias occurs.

Given that the unit of analysis is the NH, the risk of loss to follow-up is deemed inexistent. Data collection will take place in the same way as it already routinely does in a satisfactory way, thus reducing the risk of missing data.

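### If a second recruitment round takes place, the physician-level guard against contamination does not extend across the two pooled rounds

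*Protocol*

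**What the plan says.** Protocol section 5.3 names shared physicians as the route of contamination and gives the guard: "all NHs sharing at least one physician will be placed in the same cluster". The step is placed in time: "after inclusion and before randomisation, NHs will be clustered by physicians". Each included cluster then gets its own entry on a uniform random list: "numbers below 0.5 will be assigned the letter A, the others the letter B". Section 5.4 relies on this clustering to stop the intervention spreading between the arms.

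A second round is held only if recruitment falls short. Section 5.2 says: "The NHs agreeing to take part in this second round will be randomised as described in section 5.3, page 13". Section 5.3 describes round 1 and adds that, for a second round, "all activities will be held the following year in the NHs participating in this second round". Section 8.2 pools the rounds, with 2017 as the baseline year for round 1 and 2018 for round 2. The SAP (Data preparation) also pools 2017 and 2018.

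Section 5.4 further allows control NHs "to enact the intervention one year after the start of the study".

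Neither document compares the physicians of the two rounds, links an allocation across rounds, or sets linked NHs aside in the analysis.

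**The concern.** Round-1 clusters are formed and allocated about a year before the round-2 NHs are known. If the same steps are then run on the round-2 NHs, a physician can take part in a deprescribing session through a round-1 intervention NH and also be responsible for a round-2 control NH. Clustering was introduced to prevent exactly this, and because the rounds are pooled it has to hold across both.

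The delayed offer adds a second path. The synopsis has the project starting in December 2017, so one year on is about December 2018, when round-2 controls are about to begin their follow-up year. A physician shared by a round-1 control and a round-2 control can then be exposed mainly during follow-up.

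At stake are the contrast between the arms in the pooled primary and co-primary analyses, and the standard error, since NHs linked across rounds would be treated as independent.

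**Working it through.** The plan gives no figure on this point, so there is none to reproduce.

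**1. Calendar** (Schedule of assessments, sections 5.2 and 8.2)
- Round 1: baseline 2017, sessions December 2017 to January 2018, follow-up 2018.
- Round 2: randomisation October 2018, baseline 2018, sessions December 2018 to January 2019, follow-up 2019.

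**2. Allocation of a linked pair.** Take one round-1 cluster and one round-2 cluster that share a physician. With independent draws at 0.5, each combination has probability 0.5 × 0.5 = 0.25:

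| Round 1 | Round 2 | Probability | Consequence |
|---|---|---|---|
| Intervention | Control | 25% | Control exposed in its 2018 baseline and in 2019 |
| Control | Control | 25% | Control exposed mainly in 2019, if the round-1 NH takes up the offer |
| Intervention | Intervention | 25% | Round-2 baseline already exposed |
| Control | Intervention | 25% | Overlap with round-1 follow-up of about one month at most |

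The number of links m is not given. For assumed independent links, the chance of at least one round-1 intervention/round-2 control pair is 1 − 0.75^m: 25% for m = 1, 44% for 2, 58% for 3, 76% for 5 and 94% for 10.

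**3. Direction.** Let s1 and s2 be the fall in the inappropriate-medication proportion that spill-over causes in a round-2 control NH in 2018 and 2019. Section 8.3 models the change with baseline as a covariate. This gives the same group coefficient as modelling the 12-month value adjusted for baseline. With equal standard deviations at both times (assumed in section 8.1) the baseline slope is ρ, so the exposed control NH appears to improve by s2 − ρ·s1.
- Round-1 intervention route, constant spill-over (s1 = s2 = s): s(1 − ρ). With the protocol's ρ = 0.54 this is 0.46s; with 0.3 it is 0.70s; with 0.7 it is 0.30s. This is dilution, but reduced.
- Same route, fading spill-over: if s2 is below ρ·s1 (below 54% of the 2018 level at ρ = 0.54), the sign reverses and the effect is inflated.
- Delayed-offer route: s1 is close to 0, so the shift is about s2. This is dilution, close to in full.

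**4. Scale per exposed NH.** Section 8.1 has 33 NHs per group and a target difference of 4.6 points. One control NH that takes on the whole effect in follow-up only (an assumption) moves the control mean by 4.6/33 = 0.14 points, or 3.0% of the effect. At half the effect it is 2.3/33 = 0.07 points. On the round-1 intervention route with constant full spill-over it is 0.46 × 0.14 = 0.06 points. With the synopsis figure of 31 per group, the first value is 4.6/31 = 0.15 points. The total is this value times a number of exposed NHs that the documents do not give.

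**The case against.** - **The clustering rule is not limited to a round.** No sentence says that clusters are formed within each round alone, and the text on repeating activities reads as a scheduling note. This is fair: the within-round reading is an inference. But round-1 clusters are already allocated when round-2 NHs join, the random list covers the included clusters, and no rule says what to do with a link. A team following the plan would make a fresh draw.
- **The harm is doubly conditional.** It needs a second round, and a physician with NHs in both. All eligible NHs are invited in round 1, and most clusters are expected to have only two NHs. This stands, and it limits what can be said about size. Links remain plausible, since the protocol knows of a possible cluster of eight NHs.
- **Dilution is not established.** A reader might infer that exposed physicians must dilute the effect by a definable percentage. The documents do not support that. They give no share of linked controls, and baseline adjustment shrinks or can reverse the bias on the round-1 intervention route. Only the delayed-offer route points clearly to dilution, and it depends on uptake.
- **The standard-error problem is wider than this.** The planned models (protocol section 8.3; SAP, Inferential analysis) have no cluster term even within a round. This is correct and a matter in its own right. What belongs here is that any cluster identifier must span both rounds.

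**Conclusion.** The concern holds, conditional on a second round. As written, the plan repeats clustering and randomisation on the round-2 NHs without regard to round-1 physicians. The guard that sections 5.3 and 5.4 rely on therefore does not cover the pooled sample. Each linked pair has a 25% chance of being round-1 intervention/round-2 control, and a further 25% chance of being control in both rounds and open to the delayed offer.

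The total bias cannot be sized from the documents. On the stated assumptions, each exposed control NH is worth at most about 0.14 points of the 4.6-point target. The direction is uncertain on the first route and towards dilution on the second.

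It would go too far to say that contamination has occurred or that the trial is biased to the null. The second round is optional in the protocol. The SAP's unconditional pooling of 2017 and 2018 suggests that two rounds were expected, but does not report that linked NHs were enrolled.

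**What to change.** 1. Before round-2 randomisation, compare the physician lists of both rounds and report the number of links by arm. Approval by the responsible physician is already needed for enrolment, so the lists exist. If round 2 has been randomised, do this before the analysis.
2. Define physician clusters over both rounds and use that identifier for cluster-robust standard errors in the pooled analysis.
3. Pre-specify a sensitivity analysis that leaves out every round-2 NH sharing a physician with any round-1 NH, in either arm. This covers both routes and the round-2 intervention NHs with an exposed baseline.
4. State that the offer to round-1 controls opens only after 31 December of their follow-up year. This protects their own follow-up. It does not stop exposure of linked round-2 controls in 2019, which is why item 3 must include links to round-1 controls.

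Giving a linked round-2 NH the allocation of its round-1 cluster is a tempting alternative but not advisable. The allocation would be known before the NH agrees to join. Linked round-2 intervention NHs would start from an exposed baseline. The rule is also undefined for an NH whose physicians link it to both round-1 arms.

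The cost is a comparison of two lists, slightly wider standard errors and a smaller sample in the sensitivity analysis.

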Project assessments, procedures:	Participating NHs will be randomised in two groups. NHs allocated to the intervention group will hold a QC session on deprescribing, where a local consensus on the deprescribing of specific therapeutic classes will be elaborated.									
	The effects will be assessed using anonymous data on the drug consumption of the NH (already routinely collected for the administrative monitoring of the pharmaceutical assistance programme) and NH-level data on falls, hospitalisation, emergency events and death. The implementation outcomes will be evaluated with questionnaires to health care professionals of the intervention group at baseline, 3 months and 12 months.									
Number of Participants:	62 NHs will be included in this project, 31 in each group (intervention and control). Assuming a normal distribution of the reduction in PIMs proportion and a standard deviation of 7.5%, similar between the two groups, this number of participant will allow for the detection of a 20% relative reduction in the primary outcome, from 22.8% to 18.2%, with 80% power.									
Project Duration:	From December 2017 to March 2019 (possible extension to March 2020)									
Project Centre(s):	Single-centre; the intervention will take place in multiple NHs in the cantons of Vaud and Fribourg.									
Statistical Considerations:	The inclusion of 62 NH will allow for the detection of a 20% relative reduction in the use of PIMs with 80% power.									
	The main outcome will be assessed using a generalised linear regression model taking the difference at 12 months in overall PIM proportion as dependent variable. The secondary outcomes will be assessed using the same methodology. The 5% level of significance will be considered for all analyses.									
Other methodological Considerations:	No other methodological considerations.									
Risk-Benefit statement:	In previous studies of deprescribing in older people residing in nursing homes, very few adverse events occurred, none of them serious. Moreover, physicians will retain complete control over NH residents' treatments during the study. It is thus estimated that the intervention poses little to no risk compared to usual care. Possible benefits include a reduced mortality rate and fewer adverse drug reactions, as well as fewer hospital stays and reduced consumption of acute care. The risk-benefits balance of this project is estimated to be clearly positive.									

ABBREVIATIONS

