5. PROJECT DESIGN

5.1 Type of research and general project design

This project has an effectiveness-implementation hybrid design.

1) Effectiveness study:

The effectiveness is evaluated by a cluster-randomised controlled trial of an interprofessionnal quality-circle module on deprescribing. The unit of analysis for this study is the NH; all data will be aggregated at the NH level, and no data regarding individual residents will be provided to the investigators.

Participating NHs will be randomised between intervention and control groups (ratio 1:1), clustered according to their responsible physician. NHs allocated to the intervention group will hold a QC session on the topic of deprescribing and will produce a local consensus on how to deprescribe specific therapeutic classes in the NH.

2) Implementation study:

The implementation study is based on a mixed method approach combining quantitative and qualitative evaluation of the implementation strategies of the deprescribing-specific interdisciplinary quality circle module as well as the resulting deprescribing consensus. Only the intervention group will be concerned by most of the evaluations.

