8. STATISTICAL METHODOLOGY

8.1 Determination of sample size

Based on the retrospective data collected for the administrative monitoring of the Fribourg PAP, the mean proportion of PIM in the NH of Fribourg in 2015 was 22.8% (SD 6.3%). The natural year-on-year variation of the outcome was calculated between 2014 and 2015: the mean difference is 0.8% (IC₉₅ -1.1% - 2.7%, SD 5.3%); the correlation coefficient ρ between values of the outcome for 2014 and 2015 is 0.54 (IC₉₅ 0.29 – 0.72).

Studies of deprescribing have shown relative reductions in the number of PIMs ranging from 6.4% [33] to 31%[34]; one of the largest studies so far showed a 19.7% reduction in the number of PIMs [30]. Our hypothesis is that the intervention proposed in this study will reduce the proportion of PIMs used by 20%, in relative term.

We aim to detect an absolute difference of 4.6% ($22.8\% \times 0.2$) in the one-year reduction of the proportion of PIM between the control and intervention groups. The standard deviation of the difference at 12 months (SD_{diff}) was estimated with the following formula, assuming that the standard deviation at baseline and 12 months were the same and equal to 6.3%:

$$Var_{diff} = Var_{baseline} + Var_{12\;months} - 2 \cdot \rho \cdot SD_{baseline} \cdot SD_{12\;months}$$

By varying the correlation coefficient ρ along the confidence interval, plausible values of SD_{diff} were estimated to be between 4.1% (ρ =0.7) and 7.5% (ρ =0.3). A value of ρ =0.3 (SD_{diff} = 7.5%) was chosenas a conservative estimate for the calculation of the sample size, given the moderate correlation between the values for 2014 and 2015. To detect a difference between a mean difference of 0 in the control group and 4.6 in the intervention group (common SD of 7.5%, risks of α and β errors of 5% and 20%), 66NH, 33 per group, will have to be included. With an optimistic estimate of ρ = 0.7, the number of NH to include would decrease to 36. However, as this could lead to a lack of statistical power, a conservative estimate has been preferred.

Given that 82 NH meet inclusion criteria in the canton of Vaud and 42 in the canton of Fribourg, we expect that approximately 2/3 of the participants will be recruited in Vaud, and 1/3 in Fribourg.

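### Physician clusters of unequal size are allocated by unrestricted 0.5 draws although the plan assumes equal arms; a constrained random draw would remove the risk of a severe imbalance at little cost

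*Protocol*

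**What the plan says.** Section 5.1 of the protocol sets the ratio: "Participating NHs will be randomised between intervention and control groups (ratio 1:1), clustered according to their responsible physician". The synopsis fixes the arm sizes: "62 NHs will be included in this project, 31 in each group (intervention and control"). Section 8.1 also assumes equal arms, with a different total: "66NH, 33 per group, will have to be included".

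Section 5.3 describes the mechanism. NHs that share a physician form one cluster, and "NHs sharing no physician with another will be placed in clusters of size one". A list of uniform random numbers is generated, and "numbers below 0.5 will be assigned the letter A, the others the letter B". The unit of allocation is the cluster: "The list will be of the same length as the list of included NHs clusters". On sizes, the section says only that "the largest possible cluster we are aware of regroups eight NH; most clusters will only include two NHs". It concedes that the groups may be unequal because cluster sizes vary, and concludes that "this should not lead to a dramatic unbalance between the two groups".

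Section 5.2 sends a second recruitment round through the same procedure. No blocking, stratification or limit on arm totals appears in the protocol or the SAP. The primary model (protocol section 8.3; SAP, Inferential analysis) contains group and baseline value, but not canton or mission.

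**The concern.** Independent draws fix the probability of each arm at one half. They do not fix the number of clusters per arm, and still less the number of NHs, because clusters move as wholes. The protocol attributes possible inequality only to variable cluster size, but some 30 to 60 independent draws already vary by chance, and pairs and larger clusters widen that variation.

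Three things are at stake. The power calculation assumes equal arms. Canton is uncontrolled in both allocation and model, although section 8.1 expects about one third of participants from Fribourg and section 8.3.1 plans analyses by canton. The implementation study draws mainly on the intervention arm, so a small intervention arm would also weaken it.

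**Working it through.** **Inputs.** Total 62 NHs, 31 per arm (synopsis). Difference 4.6 points and SD of change 7.5 (section 8.1). Two-sided α of 0.05 (section 8.3). One draw at 0.5 per cluster; largest known cluster eight, most two, minimum one (section 5.3). The full size distribution is not given, so the scenarios below are assumptions.

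**The plan's own sample size.** n per arm = 2(z_α + z_β)² × 7.5² / 4.6².
- One-sided 5%: 2 × (1.645 + 0.842)² × 56.25 / 21.16 = 32.9, so 33 per arm. This reproduces the 66 of section 8.1.
- Two-sided 5%: 2 × (1.960 + 0.842)² × 56.25 / 21.16 = 41.7, so 42 per arm.
- The synopsis figure of 31 per arm does not reproduce: normal-approximation power is 77.9% one-sided and 67.5% two-sided.

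That shortfall is a separate matter. It matters here only as the starting point for power.

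**Distribution of arm size.** With cluster sizes m₁, …, m_C, the number of NHs in arm A has mean 31 and SD ½√(Σm²). I computed the exact distribution by convolution. A split of 2:1 or worse means at least 42 of 62 NHs in one arm.

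Example, one cluster of eight and 27 pairs: SD = ½√(64 + 27 × 4) = 6.56. The arm with the eight reaches 42 if it receives at least 17 pairs. The other arm reaches 42 if it receives at least 21. With X binomial(27, 0.5), P(X ≥ 17) + P(X ≥ 21) = 0.1239 + 0.0030 = 12.7%.

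| Assumed clusters (62 NHs) | 2:1 or worse | 60:40 or worse | Average power |
|---|---|---|---|
| 62 single NHs | 0.7% | 9.8% | 65.4% |
| 31 pairs | 7.1% | 28.1% | 64.7% |
| one eight, 13 pairs, 28 singles | 7.4% | 29.8% | 64.4% |
| one eight, 27 pairs | 12.7% | 37.7% | 64.1% |
| 8, 6, 4, 4 and 20 pairs | 17.4% | 42.4% | 63.6% |

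With one eight and 27 pairs, the central 95% range is 18 to 44 NHs in one arm, the chance of a gap of 10 NHs or more is 56%, and 31:31 cannot occur. At 66 NHs (one eight, 29 pairs) the 2:1 figure is 13.7%.

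**Power at a given split.** Two-sided t-test with noncentrality 4.6 / (7.5√(1/a + 1/b)) on 60 degrees of freedom, treating NHs as independent, as the plan does.
- 31:31: 4.6 / (7.5 × 0.2540) = 2.415, power 66.1%.
- 20:42: 4.6 / (7.5 × 0.2717) = 2.258, power 60.3%.

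The last column of the table averages this power over each distribution. The loss from 66.1% is 0.7 points with all singles, 1.5 with all pairs, 2.1 with one eight and 27 pairs, and 2.6 in the last row.

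**Canton.** One third of 62 is about 21 NHs from Fribourg. The chance that they split 14:7 or worse is 19% if all are single clusters and 34% if they form ten pairs and one single (assumed structures).

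**The case against.** The strongest reply is that simple randomisation is valid, that the protocol discloses unequal groups, and that 1:1 is naturally read as equal probability, which a cut at 0.5 delivers. The protocol says that a dramatic imbalance should not occur; it does not say that it cannot. Even with one eight and 27 pairs, about 87% of allocations are better than 2:1. All of this stands. A reader might infer that the protocol contradicts itself, but the documents do not support that: 31 per group is a planning figure, and the gap is a reassurance without a calculation.

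The risk may also be lower than the pairs scenarios suggest. Clusters are formed after inclusion, and 62 is half of the 124 eligible NHs (82 + 42), so many clusters would enter incomplete. If the 124 were one eight and 58 pairs and 62 joined at random, there would be about 45 clusters and the 2:1 chance would be about 4%. This too is an assumption. A reader might take 13% as an upper limit, but several larger clusters give 17%.

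The average loss is small, unequal arms do not bias the estimate, and baseline adjustment already covers an obvious prognostic variable. The documents give no figure for the effect of canton on the outcome, so harm from canton imbalance is possible but not shown.

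Finally, the SAP speaks of allocation in the past tense, so a new procedure may come too late for at least one round. That limits what can be changed, and the fix allows for it.

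**Conclusion.** The point holds as a low-cost improvement. The plan assumes equal arms, uses a mechanism that does not control them, and offers no calculation for its view that imbalance will be limited. At 62 NHs the chance of 2:1 or worse runs from 0.7% to about 17% over the scenarios examined, and is 7% to 13% with one cluster of eight plus pairs and singles. No single figure can be defended without the cluster list. The expected cost is about 1 to 2.5 points of power; the cost in a bad draw is about 6 points (66% to 60% at 20:42).

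Two stronger conclusions should not be drawn. The allocation does not invalidate or bias the comparison. Nor does it explain why two-sided power at 31 per arm is 66% and not 80%; that comes from the sample-size calculation and would remain with perfectly equal arms.

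**What to change.** For any round not yet allocated, replace the independent draws with a constrained random draw. List the clusters, generate the allocations whose NH totals differ by no more than a small preset number (for example two) and are approximately balanced within canton, and choose one at random. Section 5.3 forms all clusters before randomisation, so the full list is available. Enough randomness remains: with one eight and 27 pairs, before any canton restriction, 2 × [C(27,11) + C(27,12)] = 2 × (13,037,895 + 17,383,860) = 60,843,510 allocations give 30:32 or 32:30. Power at 30:32 is 66.1%, the same as at 31:31 to one decimal.

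Permuted blocks by cluster size alone would not do this. A lone cluster of eight is its own stratum, and incomplete blocks leave NH totals unbounded.

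Add canton to the primary model, because the allocation would then depend on it. For a round already allocated, add canton as a covariate, and report the realised split by arm and canton with the power at that split. Record the model change in the SAP before the allocation is unblinded.

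The cost is a few lines of Stata, a slightly more complex procedure to document, and one model term. Predictability is a minor issue because each round is allocated as a batch.
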